11.6.11. RVp-LVs Interval Test

The data collected in this section will be used for future product feature enhancement or development, and are not associated with the primary and ancillary objectives. A deviation is not required if the test is not performed or the ECG/EGM strips are not sent to BSC.

Set the EGM channels to RA, RV and LV, pacing mode to VVI, LRL to 10 to 15 beats above the subject's intrinsic rate and ventricular pacing chamber to RV Only. Obtain the ECG/EGM strips at the paper speed of 100 mm/s for approximately 3-5 representative beats in two LV sense vector configurations: LVTip1 to Can and LVRing2 to Can, respectively. Record the Subject ID, visit information (Enrollment, 6 Month, or 12 Month), and the

cathode of the LV sensing configuration (LVTip1 or LVRing2) on each ECG/EGM strip. Copies of all ECG/EGM strip should be submitted to BSC quarterly or more frequently, and before study ends.

11.6.12. SmartVector Operation

For subjects who receive the LV MSP therapy, it is required to use SmartVector to obtain recommendations for the LVa and the LVb pacing vectors after performing the LV VectorGuide tests. It is recommended to use the pacing vectors recommended by SmartVector test; however, final selection of the 2 pacing vectors is per investigator discretion.

The following values are required to be collected for subjects who have the LV MSP turned on:

- The pacing configuration of LVa and LVb, both recommended and final programmed vectors.
- Rationale if the SmartVector recommendations are not followed

The following document is required to be collected for subjects who have the LV MSP turned on:

- Print a copy of the Settings Changes Report from the PRM before setting changes are made and programmed to show the recommended changes to the LVa and LVb vector.

11.6.13. SmartOffset Operation

For subjects who receive the LV MSP therapy, it is required to use SmartOffset to obtain recommendations for the offset value between LVa, LVb, and RV. It is recommended to use the offset recommended by the SmartVector operation; however, the final programmed offset is per investigator discretion.

The following values are required to be collected for subjects who have the LV MSP turned on:

- Offset from LVa to LVb to RV, both recommended and final programmed.
- Offset from LVa to LVb if LV only pacing is programmed, both recommended and final programmed.
- Rationale if the SmartOffset recommendations are not followed

The following document is required to be collected for subjects who have the LV MSP turned on:

- Print a copy of the Settings Changes Report from the PRM before setting changes are made and programmed to show the recommended changes to the offset.

11.6.14. LV MSP Settings Programming

At the end of the 12 Month Visit, programming the device to the LV MSP feature for all subjects is per investigator discretion.

11.6.15. Battery Consumption

The following values are required to be collected:

- Time to explant
- Charge Remaining

11.6.16. Final device settings and status

Print a copy of the Device Settings Report from the PRM for all subjects at the 12 Month Visit. Final programming at the 12 Month Visit is per investigator discretion.

11.6.17. Adverse Event Assessment

Study required adverse event data will be collected and assessed for each subject. Hospitalization records are required to be sent to BSC. See **Section 20** for Adverse Event collection and reporting requirements.

11.6.18. HeartLogic Alert

The HeartLogic Alert feature is newly available in the Resonate family of devices. If the HeartLogic Alert feature is turned on, then the HeartLogic Alert(s) that resulted in a change in the subject's medical treatment will be collected.

11.6.19. "Save All" Device Data

Device data is required to be downloaded on a USB disk using "Save All" method if the subject is not enrolled in the LATITUDE Remote Monitoring System. Downloading the data requires ending the PRM session with the device. Hence, it is recommended to complete all other study activities that require PRM-device communication prior to this step. For subjects enrolled in the LATITUDE Remote Monitoring System, device data will be transmitted to BSC automatically on a regular basis and do not require manual download.

The original USB disk will be retained at the site and a copy of the disk should be submitted to BSC quarterly or more frequently. Label the Subject ID and visit information (6 Month or 12 Month) on both USB disks. The data collected in this section will be used for future product feature enhancement or development, and are not associated with the primary and ancillary objectives. A deviation is not required if the "Save All" USB disk is not performed or submitted to BSC.

A summary of the source documentation required at the 12 Month Visit is described in **Table 11.6-1**.

Table 11.6-1: Source Documentation Requirement at the 12 Month Visit

Source Documentation Requirement	Disposition
NYHA class assessment	Retain at study site
Patient Global Assessment	
Physician Global Assessment	
Adverse event assessment	
Device Settings Report, Settings Changes Report, Quick Notes Report, LV VectorGuide Report	
Hospitalization record	
Echo measurement, if performed per standard of care	
Manually recorded Charge Remaining	
ECG/EGM Strips from the SmartDelay test	Retain at study site Submit 1 copy to BSC
ECG/EGM Strips from the RVp-LVs interval test	
“Save All” device data USB disk, if applicable	

11.7. Additional Visit

An Additional Visit is required to be completed when the device is interrogated and any of the following programming settings have been permanently changed:

- Any time the device counter is reset
 - Date the counter is reset
 - Percent of LV pacing prior to resetting the counter in subjects receiving either conventional CRT or LV MSP pacing.
- AV delay
- Pacing chamber (BiV pacing or LV only pacing)
- LV Offsets
- The LV pacing configuration selected at the Enrollment Visit
- The 2 pacing vectors selected for the LV MSP at the 6 Month Visit
- SmartOffset
- Pacing mode (e.g. DDD, VVI)
- LRL

- LV MSP programming change (On or Off)

A rationale for the setting changes is required. A deviation is required if the changes in programming settings are not per the protocol requirement.

The following documents are required:

- Print a copy of the Settings Changes Report from the PRM.
- Print a copy of the Device Settings Report from the PRM.

Lead measurement is optional at this visit.

11.7.1. Adverse Event Assessment

Study required adverse event data will be collected and assessed for each subject. Hospitalization records are required to be sent to BSC. See **Section 20** for Adverse Event collection and reporting requirements.

A summary of the source documentation required at the Additional Visit is described in **Table 11.7-1**.

Table 11.7-1: Source Documentation Requirement at Additional Visit

Source Documentation Requirement	Disposition
Settings Changes Report, Device Settings Report	Retain at study site
Adverse event assessment	

11.8. Study Completion

All subjects will be followed until the completion of their required last visit, death, or withdrawal if it occurs prior to the last required visit. For subjects in the Responder Group, their last visit is the 6 Month Visit; for subjects in the Non-Responder Group, their last visit is the 12 Month Visit, regardless if the LV MSP feature was turned on or not. Upon completion of participation in the study, subjects will be followed per normal standard of care.

12. Statistical Considerations

12.1. SMART MSP Study Endpoints

12.1.1. Primary Safety Endpoint: LV MSP feature-related complication-free rate

The primary safety endpoint will be assessed for all non-responder subjects with the LV MSP on for any duration between the 6 Month Visit and the 12 Month Visit.

Safety will be confirmed by evaluating the LV MSP feature-related complication-free rate (CFR) between the 6 Month Visit and 12 Month Visit. For the purpose of this endpoint, an LV MSP feature-related complication will be defined as those complications that are

determined as “yes, related” or “possibly related” to the LV MSP feature and will count against this endpoint. These may include but are not limited to:

- Ventricular Tachyarrhythmia/Ventricular Fibrillation (VT/VF)
- Loss of Capture (LOC)
- Phrenic Nerve Stimulation (PNS)
- Worsening HF

12.1.1.1. Hypotheses

The following hypotheses will be used to evaluate the Primary Safety Endpoint:

H_0 : LV MSP feature-related complication-free rate between 6 Month Visit and 12 Month Visit $\leq 90\%$

H_A : LV MSP feature-related complication-free rate between 6 Month Visit and 12 Month Visit $> 90\%$.

The performance goal is set at 90%, which is consistent with other product features undergoing FDA evaluation⁶.

12.1.1.2. Sample Size

The overall study sample size of 586 subjects is driven by the primary effectiveness endpoint. For further details on overall sample size and attrition see **Section 12.3**. The sample size of 61 subjects is required to evaluate the Primary Safety Endpoint. Since a power calculation cannot be directly calculated for a one group Kaplan-Meier analysis, an exact test was used. A power calculation using a sample size of 61 subjects as the non-responders with the LV MSP on was calculated based on a one-sided exact test for a single binomial proportion, using SAS Version 9.4 with the following assumptions:

- Performance goal = 90%
- Expected LV MSP feature-related CFR rate between 6 and 12 Month Visit = 98%
- Significance level = 5%
- Power = 80%

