12.1.1.3. Statistical Methods

Data from subjects who are deemed as a non-responder at the 6 Month Visit with LV MSP turned on for any duration of time from 6 Month Visit onward will be eligible for inclusion in the endpoint analysis. The LV MSP feature-related CFR between the 6 Month Visit and the 12 Month Visit will be calculated using Kaplan-Meier methodology. The evaluation period for each subject will begin at the time LV MSP was turned on (at or after the 6 Month Visit) and will continue through 180 days post-LV MSP being turned on.

⁶ BSC’s Enable MRI Clinical Study (IDE # G150181); performance goal for MR Scan related complication-free rate.

The 95% one-sided lower pointwise confidence limit of the LV MSP feature-related complication-free rate will be calculated via log-log methodology and compared to the performance goal of 90%. If the lower confidence limit exceeds 90%, the null hypothesis will be rejected.

Each subject's exact follow-up time in the period between the 6 Month Visit when the LV MSP is turned on through 180 days after the LV MSP is turned on will be included in the analysis due to the rate being calculated via Kaplan-Meier methodology. The subjects that reach the 6 Month Visit and have the LV MSP turned on but fail to reach 180 days of follow-up after the LV MSP was turned on (without experiencing an endpoint event prior to their end of follow-up in the period) will be censored at the time of their end of follow-up in the period. Because non-informative censoring cannot be assumed for these subjects, a tipping point analysis will be performed to determine the potential effects these censored subjects could have on the results if full information on each subject was present. The tipping point analysis will assign each subject that was censored between the 6 and 12 Month Visit as either having or not having an LV MSP feature-related complication. The tipping point will be determined by the point at which the endpoint results turn from passing (null hypothesis) to failing (null hypothesis rejected). An exact binomial test will be performed for the tipping point analysis.

In addition, a sensitivity analysis on the impact of "Unknown" related to the LV MSP feature will be performed. Subjects with a complication determined as "yes, related", "possibly related" or "Unknown" related to the LV MSP feature will be included as a LV MSP feature-related complication.

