19.3. Risks associated with Participation in the Clinical Study

All subjects have previously received a CRT-D device implantation as part of standard of care treatment. The study procedure starts at the Enrollment Visit, which is after device implant, and at the regularly scheduled standard of care follow-up visits.

In the SMART MSP study, a subset of the subjects in the Non-Responder Group (approximately 110 subjects) will receive the LV MSP therapy from the 6 Month Visit to the 12 Month Visit. The LV MSP feature may increase the device battery consumption. It is anticipated that the impact to the battery consumption during the study may average 6 weeks but may be as long as 4.8 months.

Additionally, there may be a temporary increase in the subject's heart rate and loss of AV synchrony due to VVI pacing during the Smart Delay test and RVp-LVs interval test. In rare cases, subjects may experience temporary symptoms of fatigue, chest discomfort, dyspnea, cough, confusion, presyncope, or syncope during these tests. The investigator may stop the test if the subject does not tolerate the testing procedure.

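### The safety minimum of 61 subjects (80% power) comes from an exact binomial stand-in; under the Kaplan-Meier log-log rule that decides the endpoint, 61 gives about 65%, though the roughly 134 expected give about 99%

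*Combined protocol and SAP*

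**What the plan says.** Section 12.1.1.2 states "The sample size of 61 subjects is required to evaluate the Primary Safety Endpoint". It explains the method openly: "Since a power calculation cannot be directly calculated for a one group Kaplan-Meier analysis, an exact test was used". The inputs are a performance goal of 90%, an expected complication-free rate of 98%, a 5% level and 80% power. The same section says that the overall size of 586 is set by the effectiveness endpoint.

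Section 12.1.1.3 gives the analysis. The rate "will be calculated using Kaplan-Meier methodology" over 180 days from the time LV MSP is turned on. Then "The 95% one-sided lower pointwise confidence limit of the LV MSP feature-related complication-free rate will be calculated via log-log methodology", and the null hypothesis is rejected if that limit is above 90%. In this section the exact binomial test is assigned only to the tipping-point analysis.

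The safety set (Table 12.4-1) is every non-responder with LV MSP on for any duration. The Synopsis flowchart expects 158 non-responders at 6 months, of whom 24 lack two viable vectors. Section 19.3 says of exposure: "approximately 110 subjects) will receive the LV MSP therapy from the 6 Month Visit to the 12 Month Visit".

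**The concern.** A sample size and power should describe the rule that will be applied to the data. Here the size comes from one rule and the decision from another, and at exactly 61 subjects the two differ by one allowed complication. Success requires both primary endpoints to pass (12.4.1), so the stated safety power is part of the case for the design. Someone who later took 61 as the smallest adequate safety set would be relying on a power that the log-log rule does not give at that size. Section 12.1.1.2 also reports no power at the number of subjects actually expected to have LV MSP on.

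**Working it through.** **Inputs.** From 12.1.1.2: n = 61, goal 90%, expected rate 98%, level 5%. From 12.1.1.3: one-sided 95% log-log limit, pass if above 90%. From 12.3 and the Synopsis flowchart: 10% exit before 6 months, 70% responders, 15% without two viable vectors, 8% exit between 6 and 12 months. X is the number of subjects with a complication.

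**1. The plan's own figure.** The exact test passes with at most c complications, where c is the largest count with P(X ≤ c | n, 0.10) ≤ 0.05.
- n = 60: c = 1, power P(X ≤ 1 | 60, 0.02) = 66.2%.
- n = 61: P(X ≤ 2 | 61, 0.10) = 4.91%, so c = 2; power P(X ≤ 2 | 61, 0.02) = 87.7%.

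So 61 is the smallest size with at least 80% exact power. The figure reproduces: 80% is the target and 87.7% is what the exact test attains.

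**2. The rule in 12.1.1.3, full follow-up.** With d complications among n subjects, S = 1 − d/n, SE = √(d / [n(n − d)]) / |ln S|, and the limit is S^exp(1.645 × SE).
- n = 61, d = 1: limit 91.8%, pass.
- n = 61, d = 2: S = 59/61 = 0.9672; |ln S| = 0.03334; SE = √(2/(61 × 59)) / 0.03334 = 0.707; exp(1.645 × 0.707) = 3.20; limit 0.9672^3.20 = 89.88%, fail. The exact limit for the same data is 90.04%, pass.

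Only 0 or 1 complication can pass, so power is P(X ≤ 1 | 61, 0.02) = 65.5%, and the attained level is 1.3%. A 40,000-run simulation gave 65.3% with full follow-up and 66.9% with 8% exits uniform over 180 days.

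**3. Smallest size with 80% power under the log-log rule.**
- Full follow-up: at n = 62, two complications give 90.04%, so they pass, and power is 87.2%. The minimum is 62.
- 8% uniform exits (assumed pattern), simulated power: 68% at 62, 72% at 63, 80% at 65, 84% at 67. The minimum is about 65.

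**4. Expected safety set.** 586 × 0.90 × 0.30 × 0.85 = 134, or 158 − 24 = 134 from the flowchart. At n = 134, 7 complications give a limit of 90.49% (pass) and 8 give 89.57% (fail). Power is P(X ≤ 7 | 134, 0.02) = 99.4%, and 99.3% by simulation with 8% exits.

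**5. Zero complications.** At d = 0, ln S = 0 and the log-log limit is undefined. The plan states no convention, and every power above counts d = 0 as a pass. If it did not count:
- n = 61: P(X = 0) = 0.98^61 = 29.2%; power 65.5% − 29.2% = 36.3%.
- n = 134: P(X = 0) = 0.98^134 = 6.7%; power 99.4% − 6.7% = 92.7%.

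**6. The count in 19.3.** The flowchart runs 134 − 10 (exits after 6 months) − 14 (LV pacing below 93%) = 110. Both groups removed have had LV MSP turned on. So 110 is the effectiveness set, and about 134 are exposed for some duration. Even those expected to stay to 12 months number 134 − 10 = 124.

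**The case against.** The strongest defence is that nothing here is miscalculated and nothing depends on 61. The plan declares the exact test as a substitute, and its figure reproduces. The substitute is also a good one: with full follow-up the two rules allow the same number of complications at every size from 55 to 99 except 61, and again at 110, 124 and 134. Enrolment is driven by effectiveness, and 61 is neither a stopping trigger nor an analysis cut-off.

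Most of this stands. A reader might infer that the safety endpoint is underpowered or that the trial is at risk. The documents do not support that, because their own attrition gives more than twice 61 subjects and about 99% power. Nor do they support reading 61 as an arithmetical slip; it is correct for the test named.

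Two things remain. First, disclosing the stand-in does not make its figure true of the deciding rule. Power for that rule can be enumerated with full follow-up and simulated with exits, so the stated reason for a stand-in does not prevent a check. Second, the gap is not closed by one extra subject once the plan's 8% exits are allowed for, since 62 then gives only about 68%.

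The exposure count in 19.3 is a separate inconsistency. It has no bearing on the power at 61.

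**Conclusion.** The point holds as a minor correction to a stated figure. Measured by its own decision rule, the safety minimum of 61 carries about 65% power instead of 80%. That is about 15 points below the target, and about 22 below the 87.7% that the exact test attains at that size. The cause is a single borderline outcome, two complications in 61, which falls 0.12 points short of 90%. The correct minimum is 62 with full follow-up or about 65 with 8% exits, so the correction is one to four subjects.

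The result assumes a true rate of 98%, uniform timing of exits where exits are modelled, and zero complications counted as a pass. The last is the assumption that matters most, and the plan needs to settle it.

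**What to change.** - **12.1.1.2:** restate the size under the log-log rule: minimum 62 with full follow-up, or about 65 with 8% exits (stating the assumed exit pattern). Give the expected safety set of about 134, with up to 7 complications passing under full follow-up and power about 99% at a 98% rate. Drop the statement that a stand-in was needed, or say that power was found by enumeration or simulation.
- **12.1.1.3:** state that zero complications counts as a pass, for example by using the exact binomial lower limit in that case.
- **19.3:** reconcile the figure of approximately 110 with the roughly 134 subjects whom the attrition figures imply will have LV MSP turned on.

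The cost is a few lines of text in three sections. Enrolment, visits and data collection are unaffected.

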12.1.1.3. Statistical Methods

Data from subjects who are deemed as a non-responder at the 6 Month Visit with LV MSP turned on for any duration of time from 6 Month Visit onward will be eligible for inclusion in the endpoint analysis. The LV MSP feature-related CFR between the 6 Month Visit and the 12 Month Visit will be calculated using Kaplan-Meier methodology. The evaluation period for each subject will begin at the time LV MSP was turned on (at or after the 6 Month Visit) and will continue through 180 days post-LV MSP being turned on.

⁶ BSC’s Enable MRI Clinical Study (IDE # G150181); performance goal for MR Scan related complication-free rate.

The 95% one-sided lower pointwise confidence limit of the LV MSP feature-related complication-free rate will be calculated via log-log methodology and compared to the performance goal of 90%. If the lower confidence limit exceeds 90%, the null hypothesis will be rejected.

Each subject's exact follow-up time in the period between the 6 Month Visit when the LV MSP is turned on through 180 days after the LV MSP is turned on will be included in the analysis due to the rate being calculated via Kaplan-Meier methodology. The subjects that reach the 6 Month Visit and have the LV MSP turned on but fail to reach 180 days of follow-up after the LV MSP was turned on (without experiencing an endpoint event prior to their end of follow-up in the period) will be censored at the time of their end of follow-up in the period. Because non-informative censoring cannot be assumed for these subjects, a tipping point analysis will be performed to determine the potential effects these censored subjects could have on the results if full information on each subject was present. The tipping point analysis will assign each subject that was censored between the 6 and 12 Month Visit as either having or not having an LV MSP feature-related complication. The tipping point will be determined by the point at which the endpoint results turn from passing (null hypothesis) to failing (null hypothesis rejected). An exact binomial test will be performed for the tipping point analysis.

In addition, a sensitivity analysis on the impact of "Unknown" related to the LV MSP feature will be performed. Subjects with a complication determined as "yes, related", "possibly related" or "Unknown" related to the LV MSP feature will be included as a LV MSP feature-related complication.

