Follow-up Schedule	
Study visits in clinic will occur at the following time periods:
 
 - Enrollment Visit: between 1 day and 21 days post-CRT-D implantation. - 6 Month Follow-up Visit: 183 days -30 days/+0 day after Enrollment Visit - 12 Month Follow-up Visit: 183 days -0 day/+30 days after 6 Month Visit 
 
The flowchart illustrates the study's progression. It starts with 586 subjects at the Enrollment Visit (Consent). At the 6 Month Visit (Evaluate Response), 527 subjects remain. These are split into Conventional CRT (green) and LV MSP (blue). From the LV MSP group, 70% (369 subjects) are Responders, and 30% (158 subjects) are Non-responders. At the 12 Month Visit (Evaluate Response), 110 subjects remain. From the Responders, 10% (59 subjects) were Withdrawal and 8% (10 subjects) were Exit. From the Non-responders, 15% (24 subjects) were Exit LV MSP Arm (< 2 pacing vectors) and 8% (10 subjects) were Exit LV MSP Arm (> 6 mos). A note states: *10% (14 subjects) assumed to have < 93% LV pacing are not included in Final Effectiveness Analysis.
 
 
Subjects determined to be a responder at their 6 Month Visit will complete the study. Subjects in the Non-Responder Group, including those subjects who have no LV MSP turned on, will complete the study at their 12 Month Visit.

Study Duration	The study is expected to last approximately 36 months from the first enrollment to the study closure.

SMART MSP Post Approval Study	
Inclusion Criteria	
 1. Subjects who received de novo implantation of BSC’s Resonate family of CRT-D devices with the LV MSP feature² and BSC’s ACUITY™ X4 LV Quadripolar leads. A Resonate family of CRT-D device upgrade from previous single or dual chamber pacemaker or ICD implantation is allowed. 2. Subjects must meet BSC labeled indication for CRT-D implantation³. 3. Subjects must have a functional RA lead and RV lead implanted. 4. Subjects who are willing and capable of providing informed consent 5. Subjects who are willing and capable of participating in all testing/visits associated with this clinical study at an approved clinical study center and at the intervals defined by this protocol 6. Subjects who are age 18 and above, or of legal age to give informed consent specific to state and national law

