7.1. Primary Safety Endpoint

- LV MSP feature-related complication-free rate between the 6 Month Visit and the 12 Month Visit in non-responders with the LV MSP on for any duration.

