11.5.18. HeartLogic Alert

The HeartLogic Alert feature is newly available in the Resonate family of devices. If the HeartLogic Alert feature is turned on, then the HeartLogic Alert(s) that resulted in a change in the subject's medical treatment will be collected.

11.5.19. "Save All" Device Data

Device data is required to be downloaded on a USB disk using "Save All" method if the subject is not enrolled in the LATITUDE Remote Monitoring System. Downloading the data requires ending the PRM session with the device. Hence, it is recommended to complete all other study activities that require PRM-device communication prior to this step. For subjects enrolled in the LATITUDE Remote Monitoring System, device data will be transmitted to BSC automatically on a regular basis and do not require manual download.

The original USB disk will be retained at the site and a copy of the disk should be submitted to BSC quarterly or more frequently. Label the Subject ID and visit information (6 Month or 12 Month) on both USB disks. The data collected in this section will be used for future product feature enhancement or development, and are not associated with the primary and ancillary objectives. A deviation is not required if the "Save All" USB disk is not performed or submitted to BSC.

A summary of the source documentation required at the 6 Month Visit is described in **Table 11.5-2**.

Table 11.5-2: Source Documentation Requirement at the 6 Month Visit

Source Documentation Requirement	Disposition
NYHA class assessment	Retain at study site
Patient Global Assessment	
Physician Global Assessment	
Adverse event assessment	
Device Settings Report, Settings Changes Report, Quick Notes Report, LV VectorGuide Report	
Hospitalization record	
Echo measurement, if performed per standard of care	
Manually recorded Charge Remaining	

Source Documentation Requirement	Disposition
ECG/EGM Strips from the SmartDelay test	Retain at study site Submit 1 copy to BSC
ECG/EGM Strips from the RVp-LVs interval test	
“Save All” device data on USB disk, if applicable	

11.6. 12 Month Visit

The 12 Month Visit must be performed in office at 183 -0 day/+30 days post-6 Month Visit for subjects who were classified in the Non-Responder Group at the 6 Month Visit. A list of the data to be collected at the 12 Month Visit is provided below, with further details included in the sections below.

- NYHA class assessment
- Patient Global Assessment
- Physician Global Assessment
- HF Event

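### The primary safety endpoint runs to the 12 Month Visit (day 183 to 213), but its analysis stops 180 days after LV MSP activation

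*Combined protocol and SAP*

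**What the plan says.** Section 7.1 defines the primary safety endpoint as the "LV MSP feature-related complication-free rate between the 6 Month Visit and the 12 Month Visit in non-responders with the LV MSP on for any duration". Section 12.1.1.1 states both hypotheses for the same period: "LV MSP feature-related complication-free rate between 6 Month Visit and 12 Month Visit", against 90%. The 98% planning assumption in section 12.1.1.2 and the analysis set in Table 12.4-1 also run from the 6 to the 12 Month Visit.

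Section 11.6 fixes the timing of the closing visit: "The 12 Month Visit must be performed in office at 183 -0 day/+30 days post-6 Month Visit". The synopsis gives the same window.

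Section 12.1.1.3 starts each subject's clock when LV MSP is switched on, which may be at or after the 6 Month Visit, and says that the period "will continue through 180 days post-LV MSP being turned on". It repeats the limit for the Kaplan-Meier calculation: follow-up "through 180 days after the LV MSP is turned on will be included in the analysis". Two supporting analyses are planned. A tipping point analysis covers subjects who do not reach 180 days, and a sensitivity analysis adds complications of unknown relatedness.

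**The concern.** An in-window 12 Month Visit cannot fall before day 183, yet the analysis closes at day 180. Sections 11.5.14 and 11.5.16 require LV MSP to be switched on at the 6 Month Visit for non-responders with two viable vectors, and kept on to the 12 Month Visit. For subjects who follow that schedule, the analysed period is therefore shorter than the period named in the hypothesis.

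The excluded days include the 12 Month Visit itself, when lead measurements and the adverse event assessment take place (sections 11.6.8 and 11.6.17). A feature-related complication with onset dated to that visit would be in the database but not in the primary result. Neither supporting analysis recovers it: one concerns subjects with less than 180 days of follow-up, the other only the relatedness category. What is at stake is whether the rate tested against 90% is the rate the protocol says it is testing.

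**Working it through.** **Plan's own figure.** Section 12.1.1.2 asks for 61 subjects (goal 90%, expected 98%, one-sided exact binomial test, 5% level, 80% power). With n = 61 and success defined as at most 2 events, the type I error is P(X ≤ 2 | 61, 0.10) = 0.0491 and the power is P(X ≤ 2 | 61, 0.02) = 0.877. No smaller n meets both targets, so 61 is reproduced.

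**Inputs.**
- 12 Month Visit: day V = 183 to 213 after the 6 Month Visit (synopsis, section 11.6).
- Activation: day k after the 6 Month Visit, with k = 0 on schedule (section 12.1.1.3 allows k > 0).
- End of evaluation: day k + 180 (section 12.1.1.3).
- Exposed subjects: 158 non-responders less 24 without two viable vectors = 134 (synopsis flowchart).
- Assumptions not in the plan: constant hazard, and no censoring before day 180 or before the visit.

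**Length of the gap.** Gap = V − (k + 180).
- k = 0: 183 − 180 = 3 days to 213 − 180 = 33 days. As a share of the period between visits, 3/183 = 1.6% to 33/213 = 15.5%.
- k = 3: 0 to 30 days.
- k = 10: −7 to 23 days.
- k = 33: −30 to 0 days.

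In general the gap is (3 − k) to (33 − k) days. Where it is negative, the 180-day window runs past the subject's 12 Month Visit.

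**First events left out.** With S(180) = 0.98, S(d) = 0.98^(d/180).
- S(183) = 0.9797, so 134 × (0.98 − 0.97967) = 0.04 events.
- S(213) = 0.9764, so 134 × (0.98 − 0.97638) = 0.49 events.

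These are the extremes, with every subject seen on the first or on the last allowed day. For 61 subjects the range is 0.02 to 0.22.

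**Decision boundary at n = 134.** With e events, S = (134 − e)/134, the standard error on the log-log scale is √[e/(134(134 − e))]/|ln S|, and the lower limit is S^exp(1.645 × SE).
- e = 7: S = 0.9478, SE = 0.378, limit 0.905 (pass).
- e = 8: S = 0.9403, SE = 0.354, limit 0.896 (fail).

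The exact test has the same boundary: p = 0.036 with 7 events and 0.072 with 8.

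**Chance that late events change a pass into a fail.** Let X be the events by day 180, X ~ Bin(134, 1 − S(180)), and let Y be later first events, Y | X ~ Bin(134 − X, 1 − S(d)/S(180)). The chance is P(X ≤ 7 and X + Y ≥ 8).

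| True rate at day 180 | all seen day 183 | all seen day 198 | all seen day 213 |
|---|---|---|---|
| 98% | 0.06% | 0.4% | 0.9% |
| 96% | 1.1% | 6.7% | 12.9% |

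**Effect on the sample size.** If the rate tested were S(183) or S(213) instead of 98%, the exact power at n = 61 would be 0.872 or 0.825, still above 80%.

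**The case against.** The strongest defence is that the 180-day rule is stated openly, twice, with its own start point, censoring rule and tipping point analysis. A Kaplan-Meier rate has to be read at a fixed day, and the 12 Month Visit is a 30-day window, so some day must stand for it. Day 180 is a sensible choice: every subject activated on schedule and seen in window reaches it, with 3 days to spare, whereas an estimate at day 213 would rest on few subjects still at risk. All of this stands. It justifies the fixed horizon, but not an endpoint and hypotheses that name a different one.

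A reader might infer three stronger points that the documents do not support.
- **That the rule always favours passing.** This is true only for subjects activated on schedule, because a complication-free curve cannot rise. With late activation, which section 12.1.1.3 allows, the gap can vanish or reverse.
- **That late complications are ignored altogether.** Section 11.6.17 requires adverse event assessment at the 12 Month Visit, and Table 20.4-1 requires serious adverse events to be reported through the end of the study. The events are lost to the primary estimate, not to safety reporting.
- **That reading the curve at day 183 would cure the problem.** It recovers only 3 of up to 33 days and removes the margin: a subject activated one day late and seen on day 183 has 182 days of follow-up and would be censored.

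It is also fair to say that 1.6% to 15.5% is a share of time, not of events, and that one event near the cut-off can reverse any threshold test.

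**Conclusion.** The point holds as a mismatch between the endpoint and its analysis. For subjects activated at the 6 Month Visit and seen in window, a stated rule excludes collected endpoint events from the last 3 to 33 days, and no planned analysis brings them back.

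At the plan's 98% the expected effect is small: 0.04 to 0.49 omitted first events among about 134 subjects, and a chance below 1% of turning a pass into a fail. The required 61 subjects are not called into question. The effect matters more if the feature performs worse than planned. At 96% the chance is about 1% to 13%, depending on when in the window subjects are seen. These figures assume a constant hazard, no censoring and activation on schedule. Complications clustered around the 12 Month Visit assessments would make the effect larger, and late activation would make it smaller.

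**What to change.** Restate the endpoint as the 180-day Kaplan-Meier complication-free rate after LV MSP activation. Make the change in the synopsis, section 7.1, section 12.1.1 with its hypotheses and its 98% assumption, and Table 12.4-1, so that the rate named is the rate tested.

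Add to section 12.1.1.3 a pre-specified sensitivity analysis that counts every LV MSP feature-related complication from activation through each subject's actual 12 Month Visit, per subject, with an exact binomial test against 90%. State in advance how subjects who leave before that visit enter the denominator.

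The cost is wording changes and one supportive analysis, with no new visits, data or subjects. The downside is that the supportive rate may be slightly lower than the primary one. Both changes should be settled before the outcome data are examined.
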